9.2 PROPOSED ANALYSES

We will compare cilostazol v no cilostazol, ISMN v no ISMN, cilostazol and ISMN v neither. The proportion completing to target dose and any adverse events will be assessed using odds ratios. The LACI-2 will focus on numbers recruited, retained, tolerance and safety outcomes, blinded for TSC and unblinded intention to treat (ITT) for DMC. Safety analysis will use: Kaplan-Meier and Cox proportional regression for analysis of time-to-event outcomes of death; binary logistic regression for SAEs, recurrent stroke, MI, and in those completing 12 month MRI, the amount of microbleeds, siderosis, new infarcts, WMH burden; all adjusted for minimisation variables to maximise power.⁶⁷ We will collect data for future health economics analysis (EQ-5D-5L, EQ-VAS).

A secondary ITT analysis will be performed using logistic regression adjusted for minimisation variables of cilostazol+/-ISMN versus control on efficacy and safety outcomes, with secondary tests of subgroup interactions. Ordinal logistic regression will be used for ordinal categorical outcomes (e.g. mRS) to increase power.⁶⁸

A Statistical Analysis Plan (SAP) will be published prior to database lock and will describe analysis procedures and procedures for missing, unused or spurious data, and definitions of populations analysed.

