- Recruitment of sufficient patients, i.e. 400 patients in 24 months in the UK (and taking account of interruption due to COVID-19).
- >95% of randomised patients are retained for follow-up at one year.

Secondary outcomes - participant

Tolerability: 75% of patients will be able to tolerate trial medication, in at least half dose, up to one year after randomisation (i.e. less than 25% will stop trial medication completely through inability to tolerate the drugs).

Safety

- Symptoms of systemic or intracranial bleeding.
- The absolute risk of death, including fatal haemorrhage, does not differ significantly, i.e. fall outside the upper 95% CI of 2% per year on trial drugs versus no trial drugs, when given in addition to guideline stroke prevention drugs.
- There are no new ischaemic or haemorrhagic brain lesions or increase in SVD lesions on one year MRI significantly (at the p<0.01 level).

Efficacy

- Individual event-rates for stroke, TIA, myocardial ischaemia, cognitive impairment and dementia.
- The *combined rate* of recurrent stroke, MI, death, mild cognitive impairment (including dementia), dependency and new stroke lesions on scanning at 1 year will be 40-50% at one year after enrolment in order to allow detection of a modest but clinically-important reduction in poor outcomes in a phase III trial.
- Health economic measures include the health utility score (EQ-5D-5L) and the visual analogue score (EQVAS) at 12 months.

26b Units: Units will be shown in tables.

26c Calculations/transformations: Quality of life using UK weightings.

Brain frailty

Based on neuroimaging:

- Brain frailty = Atrophy + WML + Previous stroke lesion ⁷

- SVD score for CT = WML, lacunes; for MRI includes WMH, lacunes, PVS and microbleeds ¹⁵

Montreal cognitive assessment-modified (MoCA-m) trails

Since Trails A and B are performed, the MoCA trail is not collected but rather estimated from the Trails B score:

- If Trails B score <12 then MoCA trail = 0
- If Trails B score >=12 then MoCA trail = 1

27 Analysis methods

27a Methods

Primary endpoint

- Tabulation and graphical presentation of participant recruitment aiming for 400 participants in 24 months.
- Tabulation of retention of participants at one year aiming for >95%.

Analyses of secondary outcomes

Tabulations of:

- Tolerability to trial medications aiming for 75% of patients taking at least half dose for up to one year after randomisation.

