- Death, including fatal haemorrhage, aiming for less than outside the upper 95% CI of 2% per year.
- The *combined rate* of recurrent stroke, MI, death, cognitive impairment and dependency, aiming for 40-50% at one year after enrolment.

Comparison of rates of events between the treatment groups: cilostazol vs no cilostazol, ISMN vs no ISMN, and cilostazol and ISMN vs neither, for:

- Systemic or intracranial bleeding, recurrent cerebral and systemic vascular events, and vascular and non-vascular causes of death.
- Death, all cause.
- New ischaemic or haemorrhagic stroke lesion or increase in SVD lesions on MRI.
- Composite of: recurrent clinically-evident stroke, MI, death, cognitive impairment (including dementia) and dependency.
- Individual event: stroke (clinically-evident or imaging-detected ischaemic or haemorrhagic stroke to be reported separately), TIA, myocardial ischaemia, cognitive impairment and dementia.
- New infarcts and haemorrhages, absolute and change in WMH, microhaemorrhages, lacunes, atrophy imaging variables from central read of baseline imaging and one year MRI
- The comparisons of combined cilostazol and ISMN versus neither, whilst being very underpowered statistically, are presented since these may be the two groups studied in the planned follow-on trial.

Central tendency, comparisons and regressions will be analysed as follows (**Table D**).

Table D. Descriptive and analytical statistics

	Binary	Nominal	Ordinal	Continuous
Central tendency and distribution	N (%)	N (%)	Median [interquartile range]	Mean (standard deviation)
Comparisons	Chi-square (2x2)	Chi-square (2x2, or rxc)	Mann-Whitney U or Kruskal-Wallis	t-test (pooled) or 1-way ANOVA
Regression	Binary logistic regression (BLR)	-	Ordinal logistic regression (OLR)	Multiple linear regression (MLR)

27b Covariate adjustment: Analyses will be adjusted for minimisation covariates:

- Age, sex, stroke severity (NIHSS), dependency resulting from the stroke, systolic blood pressure, smoking status, time after stroke, years of education.

Covariate adjustment with continuous variables (age, NIHSS, SBP, time after stroke, years of education) will use original, not dichotomised, data.

27c Assumption checking: The assumption of proportionality will be tested using the likelihood test.

27d Alternative methods: If the data fail the assumption of proportionality (tested using the likelihood test), we will use alternative methods such as multiple logistic regression.

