No. microhaemorrhages (%)										
1	XX	XX (X)	XX (X)	XX (X)	XX (X)	XX (X)	XX (X)	XX (X)	XX (X)	XX (X)
2	XX	XX (X)	XX (X)	XX (X)	XX (X)	XX (X)	XX (X)	XX (X)	XX (X)	XX (X)
3	XX	XX (X)	XX (X)	XX (X)	XX (X)	XX (X)	XX (X)	XX (X)	XX (X)	XX (X)
4	XX	XX (X)	XX (X)	XX (X)	XX (X)	XX (X)	XX (X)	XX (X)	XX (X)	XX (X)
>= 5	XX	XX (X)	XX (X)	XX (X)	XX (X)	XX (X)	XX (X)	XX (X)	XX (X)	XX (X)
Type of microhaemorrhages (%)										

	N	All	ISMN	No ISMN	Cil	No Cil	ISMN + Cil	ISMN only	Cil only	None
Lobar	XX	XX (X)	XX (X)	XX (X)	XX (X)	XX (X)	XX (X)	XX (X)	XX (X)	XX (X)
Deep	XX	XX (X)	XX (X)	XX (X)	XX (X)	XX (X)	XX (X)	XX (X)	XX (X)	XX (X)
Both	XX	XX (X)	XX (X)	XX (X)	XX (X)	XX (X)	XX (X)	XX (X)	XX (X)	XX (X)
Superficial siderosis present	XX	XX (X)	XX (X)	XX (X)	XX (X)	XX (X)	XX (X)	XX (X)	XX (X)	XX (X)
Siderosis focal	XX	XX (X)	XX (X)	XX (X)	XX (X)	XX (X)	XX (X)	XX (X)	XX (X)	XX (X)
Siderosis disseminated	XX	XX (X)	XX (X)	XX (X)	XX (X)	XX (X)	XX (X)	XX (X)	XX (X)	XX (X)
Siderosis location										
Left	XX	XX (X)	XX (X)	XX (X)	XX (X)	XX (X)	XX (X)	XX (X)	XX (X)	XX (X)
Right	XX	XX (X)	XX (X)	XX (X)	XX (X)	XX (X)	XX (X)	XX (X)	XX (X)	XX (X)
Both	XX	XX (X)	XX (X)	XX (X)	XX (X)	XX (X)	XX (X)	XX (X)	XX (X)	XX (X)
Atrophy										
Brain tissue volume reduction	XX	XX (X)	XX (X)	XX (X)	XX (X)	XX (X)	XX (X)	XX (X)	XX (X)	XX (X)
Central brain tissue volume										
Modest	XX	XX (X)	XX (X)	XX (X)	XX (X)	XX (X)	XX (X)	XX (X)	XX (X)	XX (X)
Severe	XX	XX (X)	XX (X)	XX (X)	XX (X)	XX (X)	XX (X)	XX (X)	XX (X)	XX (X)
Cortical brain tissue volume										
Modest	XX	XX (X)	XX (X)	XX (X)	XX (X)	XX (X)	XX (X)	XX (X)	XX (X)	XX (X)
Severe	XX	XX (X)	XX (X)	XX (X)	XX (X)	XX (X)	XX (X)	XX (X)	XX (X)	XX (X)
White Matter hyperintensities (%)										
White matter hyperintensities	XX	XX (X)	XX (X)	XX (X)	XX (X)	XX (X)	XX (X)	XX (X)	XX (X)	XX (X)
Anterior white matter lucency										
Restricted region adjoining ventricles	XX	XX (X)	XX (X)	XX (X)	XX (X)	XX (X)	XX (X)	XX (X)	XX (X)	XX (X)
Covering ventricle to cortex	XX	XX (X)	XX (X)	XX (X)	XX (X)	XX (X)	XX (X)	XX (X)	XX (X)	XX (X)
Posterior white matter lucency										
Restricted region adjoining ventricles	XX	XX (X)	XX (X)	XX (X)	XX (X)	XX (X)	XX (X)	XX (X)	XX (X)	XX (X)
Covering ventricle to cortex	XX	XX (X)	XX (X)	XX (X)	XX (X)	XX (X)	XX (X)	XX (X)	XX (X)	XX (X)
Anterior and/or Posterior white matter lucency										

	N	All	ISMN	No ISMN	Cil	No Cil	ISMN + Cil	ISMN only	Cil only	None

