Partially cavitated - FLAIR cavity but not=CSF	XX	XX (X)	XX (X)	XX (X)	BLR	XX	XX (X)	XX (X)	BLR	XX	XX (X)	XX (X)	BLR	XX
Partially cavitated - FLAIR=WMH T2=cavity	XX	XX (X)	XX (X)	XX (X)	BLR	XX	XX (X)	XX (X)	BLR	XX	XX (X)	XX (X)	BLR	XX
Partially cavitated - visible on T2 not FLAIR	XX	XX (X)	XX (X)	XX (X)	BLR	XX	XX (X)	XX (X)	BLR	XX	XX (X)	XX (X)	BLR	XX
Not cavitated (WML-like)	XX	XX (X)	XX (X)	XX (X)	BLR	XX	XX (X)	XX (X)	BLR	XX	XX (X)	XX (X)	BLR	XX
Disappeared	XX	XX (X)	XX (X)	XX (X)	BLR	XX	XX (X)	XX (X)	BLR	XX	XX (X)	XX (X)	BLR	XX
Become visible	XX	XX (X)	XX (X)	XX (X)	BLR	XX	XX (X)	XX (X)	BLR	XX	XX (X)	XX (X)	BLR	XX
Never visible	XX	XX (X)	XX (X)	XX (X)	BLR	XX	XX (X)	XX (X)	BLR	XX	XX (X)	XX (X)	BLR	XX
Evidence of new stroke (%)														

	N	All	OR/MD/ p- value			OR/MD/ p- value			ISMN + Cil		OR/MD/ p- value	
			ISMN	No ISMN	(95%CI)	Cil	No Cil	(95%CI)	None	(95%CI)		
Ischaemic	XX	XX (X)	XX (X)	XX (X)	BLR XX	XX (X)	XX (X)	BLR XX	XX (X)	XX (X)	BLR	XX
Haemorrhagic	XX	XX (X)	XX (X)	XX (X)	BLR XX	XX (X)	XX (X)	BLR XX	XX (X)	XX (X)	BLR	XX
Microhaemorrhages (%)	XX	XX (X)	XX (X)	XX (X)	BLR XX	XX (X)	XX (X)	BLR XX	XX (X)	XX (X)	BLR	XX
No. microhaemorrhages (%)					OLR XX			OLR XX			OLR	XX
1	XX	XX (X)	XX (X)	XX (X)		XX (X)	XX (X)				XX (X)	XX (X)
2	XX	XX (X)	XX (X)	XX (X)		XX (X)	XX (X)				XX (X)	XX (X)
3	XX	XX (X)	XX (X)	XX (X)		XX (X)	XX (X)				XX (X)	XX (X)
4	XX	XX (X)	XX (X)	XX (X)		XX (X)	XX (X)				XX (X)	XX (X)
>= 5	XX	XX (X)	XX (X)	XX (X)		XX (X)	XX (X)				XX (X)	XX (X)
Change from baseline	XX	XX [XX, XX]	XX [XX, XX]	XX [XX, XX]	OLR XX	XX [XX, XX]	XX [XX, XX]	OLR XX	XX [XX, XX]	XX [XX, XX]	OLR	XX
Small vessel disease score												
Total	XX	XX [XX, XX]	XX [XX, XX]	XX [XX, XX]	OLR XX	XX [XX, XX]	XX [XX, XX]	OLR XX	XX [XX, XX]	XX [XX, XX]	OLR	XX
Change from baseline	XX	XX [XX, XX]	XX [XX, XX]	XX [XX, XX]	OLR XX	XX [XX, XX]	XX [XX, XX]	OLR XX	XX [XX, XX]	XX [XX, XX]	OLR	XX
Atrophy												
Brain tissue volume reduction	XX	XX (X)	XX (X)	XX (X)	BLR XX	XX (X)	XX (X)	BLR XX	XX (X)	XX (X)	BLR	XX
Central brain tissue volume					OLR XX			OLR XX			OLR	XX
Modest	XX	XX (X)	XX (X)	XX (X)		XX (X)	XX (X)				XX (X)	XX (X)
Severe	XX	XX (X)	XX (X)	XX (X)		XX (X)	XX (X)				XX (X)	XX (X)
Cortical brain tissue volume					OLR XX			OLR XX			OLR	XX
Modest	XX	XX (X)	XX (X)	XX (X)		XX (X)	XX (X)				XX (X)	XX (X)
Severe	XX	XX (X)	XX (X)	XX (X)		XX (X)	XX (X)				XX (X)	XX (X)
Change from baseline					OLR XX			OLR XX			OLR	XX

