More	XX	XX (X)	XX (X)	XX (X)		XX (X)	XX (X)				XX (X)	XX (X)
Less	XX	XX (X)	XX (X)	XX (X)		XX (X)	XX (X)				XX (X)	XX (X)
None	XX	XX (X)	XX (X)	XX (X)		XX (X)	XX (X)				XX (X)	XX (X)

	N	All	OR/MD/ HR p- value				OR/MD/ HR (95%CI)				ISMN + Cil		OR/MD/ HR p- value	
			ISMN	No ISMN	(95%CI)	Cil	No Cil	(95%CI)	None	(95%CI)				
White Matter hyperintensities (%)														
White matter hyperintensities	XX	XX (X)	XX (X)	XX (X)	BLR	XX	XX (X)	XX (X)	BLR	XX	XX (X)	XX (X)	BLR	XX
Anterior white matter lucency														
Restricted region adjoining ventricles	XX	XX (X)	XX (X)	XX (X)	BLR	XX	XX (X)	XX (X)	BLR	XX	XX (X)	XX (X)	BLR	XX
Covering ventricle to cortex	XX	XX (X)	XX (X)	XX (X)	BLR	XX	XX (X)	XX (X)	BLR	XX	XX (X)	XX (X)	BLR	XX
Posterior white matter lucency														
Restricted region adjoining ventricles	XX	XX (X)	XX (X)	XX (X)	BLR	XX	XX (X)	XX (X)	BLR	XX	XX (X)	XX (X)	BLR	XX
Covering ventricle to cortex	XX	XX (X)	XX (X)	XX (X)	BLR	XX	XX (X)	XX (X)	BLR	XX	XX (X)	XX (X)	BLR	XX
Anterior and/or Posterior white matter lucency														
Restricted region adjoining ventricles	XX	XX (X)	XX (X)	XX (X)	BLR	XX	XX (X)	XX (X)	BLR	XX	XX (X)	XX (X)	BLR	XX
Covering ventricle to cortex	XX	XX (X)	XX (X)	XX (X)	BLR	XX	XX (X)	XX (X)	BLR	XX	XX (X)	XX (X)	BLR	XX
Periventricular WMH Fazekas score							OLR	XX					OLR	XX
1	XX	XX (X)	XX (X)	XX (X)				XX (X)	XX (X)				XX (X)	XX (X)
2	XX	XX (X)	XX (X)	XX (X)				XX (X)	XX (X)				XX (X)	XX (X)
3	XX	XX (X)	XX (X)	XX (X)				XX (X)	XX (X)				XX (X)	XX (X)
Change from baseline	XX	XX [XX, XX]	XX [XX, XX]	XX [XX, XX]	OLR	XX	XX [XX, XX]	XX [XX, XX]	OLR	XX	XX [XX, XX]	XX [XX, XX]	OLR	XX
Deep WMH Fazekas score							OLR	XX					OLR	XX
1	XX	XX (X)	XX (X)	XX (X)				XX (X)	XX (X)				XX (X)	XX (X)
2	XX	XX (X)	XX (X)	XX (X)				XX (X)	XX (X)				XX (X)	XX (X)
3	XX	XX (X)	XX (X)	XX (X)				XX (X)	XX (X)				XX (X)	XX (X)
Change from baseline	XX	XX [XX, XX]	XX [XX, XX]	XX [XX, XX]	OLR	XX	XX [XX, XX]	XX [XX, XX]	OLR	XX	XX [XX, XX]	XX [XX, XX]	OLR	XX
Periventricular and/or Deep WMH Fazekas score							OLR	XX					OLR	XX
1	XX	XX (X)	XX (X)	XX (X)				XX (X)	XX (X)				XX (X)	XX (X)
2	XX	XX (X)	XX (X)	XX (X)				XX (X)	XX (X)				XX (X)	XX (X)

	N	All	OR/MD/ p- value				OR/MD/ p- value				ISMN + Cil		OR/MD/ p- value	
			ISMN	No ISMN	(95%CI)	HR	Cil	No Cil	(95%CI)	HR	None	(95%CI)	HR	(95%CI)
3	XX	XX (X)	XX (X)	XX (X)			XX (X)	XX (X)			XX (X)	XX (X)		

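### SAP Table 9 tests the middle grade of the white matter lucency rating as its own yes/no outcome; that odds ratio does not measure severity, and the plan's own rule calls for one ordinal model

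*SAP*

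**What the plan says.** SAP Table 9 lists the adjudicated one-year MRI readings. It has three lucency headings: "Anterior white matter lucency", its posterior counterpart, and one for either or both sites. No model is entered on these headings. Under each, "Restricted region adjoining ventricles" and "Covering ventricle to cortex" carry separate binary logistic regressions (BLR), each with a p-value, for ISMN v none, cilostazol v none and both v neither.

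The plan's general rule differs. In SAP 27a, Table D gives the regression for ordinal data as "Ordinal logistic regression (OLR)". Protocol 9.2 says: "Ordinal logistic regression will be used for ordinal categorical outcomes (e.g. mRS) to increase power".

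Table 9 follows that rule for other graded readings. "Periventricular WMH Fazekas score" has one OLR on the heading and no test on the grade rows. So does "Central brain tissue volume", which, like lucency, prints two grades and no row for none. Microhaemorrhage number, lacune number and regional WMH change are handled the same way.

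The SAP states no reference category or cumulative coding for the lucency rows, and no reason for treating them differently.

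**The concern.** The two printed grades are ordered by extent, with no lucency below them. Restricted is then the middle of three levels. A yes/no model for that level pools the best and worst scans as its reference group. A patient who worsens from restricted to covering and one who improves from restricted to none change this outcome in exactly the same way. The odds ratio is therefore not a severity measure, and its direction depends on the grade mix as well as on the drug.

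At stake is how nine secondary MRI estimates are read, and how they look in Figure 5, which plots the Table 9 readings. One of the SAP's safety statements (26a) concerns "increase in SVD lesions on one year MRI significantly (at the p<0.01 level)", so readers will look to this part of the table for signs of harm. The covering row is a legitimate worst-v-rest split, but it ignores the difference between none and restricted and so gives up power.

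**Working it through.** The documents give no power figure or grade distribution for lucency, so there is no stated figure to reproduce. What follows is an illustration.

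**Inputs**
- Number recruited: 363 (SAP Table 2).
- Missing one-year MRI: 15%, where Protocol 9.1 says at least 15%. 363 × 0.85 = 308.55, taken as 154 per arm. This assumes that everyone enters the comparison and that arms are equal.
- Two-sided 5% (SAP 16 gives p<0.05; two-sidedness is assumed), and 1% for the MRI safety statement.
- Assumed: three exclusive levels none/restricted/covering, four control mixes, and a harmful common odds ratio of 1.8.

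**Number of tests.** 3 headings × 2 rows × 3 comparisons = 18, of which 3 × 3 = 9 are on the restricted row.

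**Restricted-row odds ratio.** For each cut, treated odds = 1.8 × control odds. The treated restricted proportion is P(restricted or worse) − P(covering).

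Worked case, control 20/40/40:
- P(restricted or worse): odds 0.80/0.20 = 4, × 1.8 = 7.2, giving 7.2/8.2 = 0.878.
- P(covering): odds 0.40/0.60 = 0.667, × 1.8 = 1.2, giving 1.2/2.2 = 0.545.
- Treated restricted = 0.878 − 0.545 = 0.333. Odds ratio = (0.333/0.667)/(0.40/0.60) = 0.75.

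Every patient-level shift here is towards worse, yet the row points to benefit.

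**Power.** 20,000 simulated trials per mix, unadjusted. Each binary row used a two-proportion z test. OLR used the tie-corrected Mann-Whitney test, which is the score test of the proportional-odds model. Repeat runs agreed to about one percentage point.

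| Control none/restricted/covering | Restricted-row OR | Power restricted | Power covering | Power OLR |
|---|---|---|---|---|
| 50/35/15 | 1.25 | 16% | 53% | 78% |
| 40/40/20 | 1.08 | 7% | 61% | 80% |
| 30/45/25 | 0.93 | 6% | 66% | 79% |
| 20/40/40 | 0.75 | 24%, nearly all towards benefit | 71% | 78% |

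The covering-row odds ratio is 1.8 throughout. At 1%, OLR has about 56% to 58% power and the covering row 28% to 50%.

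**Harm confined to restricted-to-covering.** Let control be 30/50/20 and treated 30/35/35.
- Restricted-row OR = (0.35/0.65)/(0.50/0.50) = 0.54, significant for apparent benefit in 76% of trials.
- Covering-row OR = (0.35/0.65)/(0.20/0.80) = 2.15, with about 84% power.
- OLR has about 40% power, because proportional odds fails.

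**The two rows read together.** The misleading pattern is restricted significant for benefit with covering not significant for harm. It occurs in well under 1% of trials under a common odds ratio. In the restricted-to-covering case it occurs in about 7% (about 10% at the 1% level).

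**Sensitivity to the inferred level.** If scans with no lucency were left out of the denominator, the two rows would be mirror images and the restricted row would still fall below 1 under harm. If the row were coded as restricted or worse, its odds ratio would be 1.8 in every mix above and the problem would disappear.

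**The case against.** The strongest reply is that nobody reads the restricted row alone. The covering row, with its own counts and odds ratio, sits directly beneath it. White matter worsening is also measured elsewhere in Table 9: Fazekas levels and their change from baseline by OLR, WMH change in five regions by OLR, and change in SVD score. The lucency rows are one-year levels without a change row, so their tie to an increase in lesions is indirect. This stands, and it sets the size of the point.

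A reader might infer that a harmful drug could pass as safe or beneficial because of this layout. The documents do not support that. The joint calculation shows that a false benefit signal on the restricted row almost always comes with a significant harm signal on the covering row, and the safety statement does not rest on these nine tests. Nor is the restricted row always reversed: it points to harm when most scans show no lucency, and the plan gives no grade distribution from which to say how often reversal would occur.

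Two further objections hold in part. OLR is weaker than the covering row when harm moves patients only from restricted to covering, so the covering row should stay. For the combined anterior and/or posterior heading no rule says how a scan graded differently at the two sites is classed. Its rows may overlap, and OLR cannot be applied until that is settled.

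None of this defends the restricted-row test itself.

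**Conclusion.** The point holds as an inconsistency with the plan's own analysis rule, and it has a real but limited consequence. The nine restricted-row odds ratios do not measure severity: under harm they can lie above, near or below 1 according to the grade mix. The gain from a single OLR over the covering row was 7 to 25 percentage points of power in the four common-odds-ratio mixes (78 − 71 to 78 − 53).

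This rests on the inferred none level, on exclusive grades, on assumed mixes and effect size, and on 154 v 154. The both-v-neither comparison is smaller, about 77 v 77 if the four groups are equal, so its power would be lower.

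Severity is minor to moderate. These are secondary MRI safety readings with no multiplicity adjustment, and the feasibility primary endpoint is untouched.

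**What to change.** In SAP Table 9, and correspondingly in Figure 5:

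- Under each lucency heading, drop the BLR on the restricted row. Fit one OLR on none < restricted < covering, with none printed as an explicit level and the level counts shown descriptively.
- For the combined anterior and/or posterior heading, define the grade as the worse of the two sites.
- Keep the BLR of covering v none or restricted as a labelled supplement, to protect against harm confined to the top cut.

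This changes SAP wording and table shells only and needs no new data. The number of tests stays at 18 (9 OLR plus 9 supplementary BLR), but all of them then have a direction that can be interpreted. The cost is reliance on proportional odds, already accepted for the Fazekas rows. If the authors intended the restricted row to mean restricted or worse, stating that coding would remove the directional problem, though not the departure from Table D.
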